7.3 Confidentiality

All data and records generated during this study will be kept confidential in accordance with Institutional policies and HIPAA on subject privacy and the Investigator and other site personnel will not use such data and records for any purpose other than conducting the study.

Survey and interview responses will be stored on the WTH platform. The site is HIPAA compliant. Please see Section 9.2 for measures taken to assure confidentiality.

Data regarding adherence to metered-dose inhaler use will be stored on the website of Propeller Health and transferred to the WTH platform through the integrated API. The Propeller Health site is HIPAA compliant. Please see Section 7.2 for measures taken to assure confidentiality.

No identifiable data will be used for future study without first obtaining IRB approval.

7.4 Regulatory and Ethical Considerations

7.4.1 Data and Safety Monitoring Plan

Please see Appendix 2 for the DSMP for this study. A local DSMB has been appointed for this study with guidance from the Clinical Trials Office at the NHLBI. The PI has developed a number of additional strategies to ensure the accuracy, security, and validity of the various data sources. First, identifiable information will be converted to study ID for storage and analysis. Data extracted from the Epic medical record by the research assistant and the study questionnaire responses will be entered into and stored in the WTH platform at Penn by study ID. Coded adherence data from the Propeller platform will be downloaded to the WTH platform in data downloads through the API.

Second, the data sources that will contain identifiable information, namely the Propeller and WTH platforms, will be held to the highest of security standards. Please see section 7.2 for the security features of the Propeller and WTH platforms.

Please see section 7.2 for further details of the measures in place to protect data confidentiality, especially with respect to data transfers.

7.4.2 Risk Assessment

Risks are minimal. There is no risk or discomfort to the study intervention. The study intervention merely adds electronic monitoring and text message notifications to already prescribed medications. The main risk is breach of confidentiality. Please refer to the above Sections 7.2, 7.3, and 7.4.1 for a list of strategies in place to avoid a breach of confidentiality.

7.4.3 Potential Benefits of Trial Participation

Improving adherence may lead to better control of asthma and therefore decrease school absences, parental work absences, and the number of visits to the ED or admissions to the hospitals.

7.4.4 Risk-Benefit Assessment

The risks of this study are minimal. The main risk of the study is breach of confidentiality. Methods of avoiding a potential breach of confidentiality are described above in Sections 7.2, 7.3, and 7.4.1. The potential to improve asthma adherence may improve asthma control and

decrease ED visits or hospital admissions for asthma. The potential benefits of study participation outweigh the risks.

7.5 Recruitment Strategy

7.5.1 Recruitment Strategy

Prospective subjects will be identified in the Epic medical record at CHOP. Patients with at least 2 asthma exacerbations (hospitalizations, ED visits, or outpatient visits where an oral steroid course was given for asthma) in the last year will be recruited from general pediatrics services. Epic alerts and patient lists will assist research staff in identifying eligible patients. Potential participants will be approached in-person by a trained study team member during the course of their hospital stay, at a hospital follow-up appointment, or by telephone. No more than 125 subjects will be enrolled.

7.5.2 Study Information Sheet

The study information sheet will be used as a recruitment tool to give participants information about our study. It includes a brief overview of our study and our contact information for potentially interested subjects to contact us.

7.6 Informed Consent/Accent and HIPAA Authorization

Subjects will be approached in person while in the hospital, at a hospital follow-up appointment, or by telephone and given information about the study by a trained study team member. Potential participants will not need to decide on participation right away; they may decide whether or not to participate up until the time of discharge from the hospital or end of their follow-up appointment.

Electronic consent via the REDCap platform or written consent on a physical copy of the form will be obtained following agreement to participate in the study.

To reduce low literacy barriers, the study team member will go through the consent form with the family and answer any questions pertaining to the material. Participants will be given 10-15 minutes to review the consent form on their own. This process will be done in a HIPAA compliant manner.

Assent will be obtained for children aged seven or older, as per the CHOP IRB regulations via the REDCap electronic consent platform or on a physical copy of the consent form. The study will be explained in an age-appropriate manner. This process will be done in a HIPAA compliant manner.

7.6.1 Partial Waiver/alteration of HIPAA Authorization

We request a partial waiver of HIPAA authorization under 45 CFR 164.512(i.)(2)(ii).

Study staff propose to assess patient eligibility by screening the daily census of patients admitted to a General Pediatrics service at CHOP for patients 5-12 who have an admission diagnosis of asthma and for whom the asthma pathway order is activated using the Epic medical record.

(A) The use or disclosure of protected health information involves no more than a minimal risk to the privacy of individuals, based on the following elements:

1.) Plan to protect the identifiers from improper use and disclosure:

Only authorized study staff will access the Epic medical record for screening purposes. Information from the screening will be stored in a REDCap database only used by study staff.

2.) Plan to destroy the identifiers at the earliest opportunity consistent with conduct of the research:

For those who do not consent to study inclusion, protected health information will be deleted upon the family's decline or if the family is not enrolled in the study for other reasons (unable to approach parent for consent due to lack of parental availability). For those who do consent to be enrolled in the study, HIPAA authorization for the collection of PHI will be obtained at the time of enrollment.

3.) Protected health information will not be reused or disclosed:

Protected health information will not be reused or disclosed to any other person or entity, except as required by law, for authorized oversight of the research project, or for other research for which the use or disclosure of protected health information would be permitted.

(B) The research could not practicably be conducted without a partial waiver of HIPAA authorization.

There are over 2500 admissions for asthma on yearly basis at CHOP with hospital lengths of stay generally less than 24-48 hours, and each of these cases could be potentially eligible for recruitment. Given the limited time each patient is in the hospital and the number of potential patients, it would not be feasible to consent each of these 2500 for screening of their electronic medical records for eligibility.

(C) The research could not practicably be conducted without access to and use of the protected health information.

Access to protected health information is necessary in order to assess eligibility for the study. For example, protected health information would be used to identify current inpatients, screen for eligible ages based on our inclusion criteria, subject's date of admission, primary care doctor, and whether the subject has been prescribed the specific daily controller medications which are compatible with the electronic monitoring devices.

7.6.2 Waiver of Consent

We request a Waiver of Consent under 45 CFR 46.116(d).

Study staff propose to assess patient eligibility by screening the daily census of patients admitted to a General Pediatrics service at CHOP for patients 5-12 who have at least 2 admissions for asthma OR 1 admission AND at least 1 ED visit in the last 365 days using the Epic medical record and Epic alerts and patient lists.

The research meets the criteria for a Waiver of Consent based on the following elements:

(A) The research involves no more than minimal risks to the subjects, based on the following 3 elements:

1.) Plan to protect the identifiers from improper use and disclosure:

Only authorized study staff will access the Epic medical record for screening purposes. Information from the screening will be stored in a REDCap database only used by study staff. 2.) Plan to destroy the identifiers at the earliest opportunity consistent with conduct of the research:

For those who do not consent to study inclusion, protected health information will be destroyed upon the family's decline or if the family is not enrolled in the study for other reasons (unable to approach parent for consent due to lack of parental availability). For those who do consent to be enrolled in the study, HIPAA authorization for the collection of PHI will be obtained at the time of enrollment via informed consent.

3.) Protected health information will not be reused or disclosed:

Protected health information will not be reused or disclosed to any other person or entity, except as required by law, for authorized oversight of the research project, or for other research for which the use or disclosure of protected health information would be permitted.

(B) The waiver will not adversely affect the rights and welfare of the subjects:

When potential participants are determined to be eligible for enrollment, a study team member will explain the study and ask if they would like to participate. Consent will be obtained in a HIPAA compliant manner, as described in the study procedures (see above Section 9.6). Participants will retain the right to choose whether they want to participate and provide consent. Patients who are deemed ineligible based on screening of the Epic medical record will not be approached for enrollment. The only information that will be retained for those screened ineligible will be the reason why they were deemed ineligible.

(C) The research could not practicably be carried out without the waiver:

There are over 2500 admissions for asthma on yearly basis at CHOP with hospital lengths of stay generally less than 24-48 hours, and each of these cases could be potentially eligible for recruitment. Given the limited time each patient is in the hospital and the number of potential patients, it would not be feasible to consent each of these 2500 for screening of their electronic medical records.

(D) Whenever appropriate, the subjects will be provided with additional pertinent information about participation.

Following screening using the Epic medical record, potentially eligible subjects will have the opportunity to review the study consent form and ask questions of the study team member. The Principal Investigator may also be contacted by phone if more information is needed. The consent form includes contact information, and the participants may request additional information at any time. Patients who are deemed ineligible based on screening of the Epic

medical record will not be approached for enrollment and only the reason for study ineligibility will be retained.

7.7 Payment to Subjects/Families

7.7.1 Compensation

Non-responders who do not undergo randomization will receive a \$10 disbursement for their participation and not be paid further. At the completion of Visit 1, caregiver study participants will receive an automatic debit card credited with \$20. For participants who are enrolled by telephone, they will be mailed their automatic debit card following enrollment. At the end of Study Visits 2, 3, 4, and 5, caregiver participants will be credited \$20 for each study visit, for a total of \$100. Additionally, children in Arm 1 will receive a performance-based reward payment during each month of the Experiment phase with a maximum value of \$30/month. Children randomized to Arms 2 and 3 who have any actuations recorded each month of the Experiment phase will receive a \$10 disbursement at the end of each month (for a total of \$30) and children in all study arms will receive a \$10 disbursement at the end of each month with recorded actuations during the Observation phase (for an additional \$30), none of which will be contingent upon ICS adherence.

8 PUBLICATION

Data will be analyzed by the investigators, with the help of a study statistician, and submitted for presentation at national meetings and publication in academic journals.



Appendix 1

Run-in phase text messages and automated responses:

Text 1: PARTICIPANT_FIRSTNAME, welcome to the run-in period! We will be sending you a few texts over the next 2 weeks. Please respond to these messages if they ask for a response, otherwise you may be removed from the study. Text 1 to confirm you received this text.

Automated response: Great, thank you!

Text 2: Are you having problems with the Propeller sensors or app? Text 1 for YES or 2 for NO.

If 1, automated response: Thank you for your response. A study team member will be contacting you shortly.

If 2, automated response: Great, thank you!

Text 3: Is the app getting puff information from the sensors? Text 1 for YES or 2 for NO.

If 1, automated response: Thank you for your response. A study team member will be contacting you shortly.

If 2, automated response: Great, thank you!

Text 4: Are you receiving our texts? Text 1 for YES. If you haven't responded to any of our messages, you will be removed from the study. And we want you to stay!

If 1, automated response: Great, thank you!

Experiment phase text message reminders:

1. Hi! This is your friendly daily controller inhaler reminder. Quick fact: children who take controller medication daily have fewer future asthma attacks.
2. Hello! A friendly reminder to make sure your child took their daily controller inhaler. Even for older children, parents are an important part of improving asthma control.
3. Hi! Did your child take their daily controller inhaler today? Quick fact: when taken regularly, daily controllers reduce the number of emergency room visits.
4. Hello there! Has your child taken all of their daily controller puffs today? Remember to always use a spacer with those puffs.
5. Hi! A quick reminder to make sure that your child took their daily asthma inhaler. Quick tip: have your child take their daily controller inhaler with another daily activity (tooth-brushing).
6. Hi! This is a friendly daily controller inhaler reminder for you. When taken regularly, daily inhalers reduce the number of missed school days.

7. Hello! This is your friendly daily controller inhaler reminder. Quick tip: when your child is away from home remember to send medications and a spacer with them.
8. Hi! Remind your child to take their asthma medicine. Each puff you take (as prescribed) gets you closer to your goal!
9. Hi! Did you remind your child to take their controller inhaler today?
10. Hi there! Make sure to remind your child to take their medicine today!

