2.1 Primary Objective (or Aim)

The primary objective of this study is to determine the marginal effects of financial ICS incentives on adherence (1° outcome) and healthcare system use and costs (2° outcomes) in a prospective cohort of child-caregiver dyads.

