3.1.3 Experiment Phase (Months 1-3) and Observation Phase (Months 4-6)

The three experimental conditions will be: financial incentives, adherence reminders, and feedback (Arm 1); adherence reminders and feedback without incentives (Arm 2); or electronic monitoring alone (Arm 3). The financial incentives in Arm 1 will consist of 3 months of fixed-ratio incentives for each ICS actuation (i.e. 25 cents per puff for children on 4 daily ICS doses and 50 cents per puff for children on 2 daily doses), with a maximum of \$1 per day. With regard to the reminders and feedback in Arms 1 and 2, study participants will receive automated daily text message or push notification reminders and automated weekly feedback summarizing their adherence performance through Way to Health, a mobile health, electronic monitoring platform (described below in section 4.1). At the end of the first month of the experiment phase, families will be contacted by study staff to complete a follow-up survey that will reassess disease control, medication supply, and intentions and behaviors with

regard to ICS use (study visit 2). After the experiment interval, families will be contacted again by study staff to complete a follow-up survey and a semi-structured interview (study visit 3). At this point, all reminders, feedback, and incentives will cease, but daily ICS use monitoring will continue with the electronic sensors for all study arms (*Observation* phase) to assess for enduring effects. There will be a fourth study visit in the 7th study month, when study surveys will be completed, and a fifth and final study visit at one year assessing asthma control and health care utilization outside of the CHOP system.

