4.4 Study Experiment Phase (Phase 2)

The child-caregiver dyads will be randomized into one of three arms for months 1-3: (1) receiving daily reminders, weekly feedback, and incentives, (2) receiving reminders and weekly feedback without incentives, or (3) receiving no reminders, feedback, or incentives. Participants will not know which group they are randomized to until they begin this phase of the study. Study participants will be contacted by telephone call or text message to inform them to which study arm they were randomized. At this time, study staff will help participants randomized to Arm 1 select an adherence reward goal of \$30 value.

4.5 Visit 2 (clinic or home preferred, telephone if not possible) – month 2

- Study visit 2 survey question blocks (see section 4.11.2)
- Equipment and medication refill check

4.6 Visit 3 (clinic or home preferred, telephone if not possible) – month 4

- Study visit 3 survey question blocks (see section 4.11.2)
- Semi-structured interview on intervention experiences and preferences
- Equipment and medication refill check

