4.17 Sample Size and Power

Our analysis of pilot data demonstrates a 48% difference in ICS adherence when comparing a time interval with financial incentives (the same schema proposed in this study) to a time period without incentives. To ensure a power of 80% at a significance level of 0.05 to detect a more conservative 30% difference in average adherence between arms 1 and 3 in the *Experiment* phase (corresponding to 65% and 35%, respectively), 40 patients are required in each of these two arms. To ensure scientific rigor given the vulnerable nature of the population, we estimate ~20% loss to follow-up. Therefore, we will aim to enroll 50 participants in study arms 1 and 3 and 25 participants in arm 2, or 125 participants total, to achieve sufficient power to detect a difference between arms 1 and 3. The study is not to be powered to detect differences in arms 1 to 2 or 2 to 3 (hence the 2:1:2 randomization schema) or for health outcomes or cost offset; rather, it is intended to obtain preliminary estimates of marginal effects of the intervention components and effect sizes on utilization outcomes by comparing arm 1 to 2 and 2 to 3 to power a future multicenter study. Baseline data reveals that ~50% of children with at least 2 prior hospitalizations have a repeat ED visit or inpatient stay 6 months after the 2nd hospital discharge.

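### Reminder 8 in Appendix 1 refers to a goal that only Arm 1 is given, so its wording should be made neutral in both reminder arms (minor)

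*Combined protocol and SAP*

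**What the plan says.** Section 3.1.3 defines three conditions: Arm 1 receives incentives, reminders and feedback; Arm 2 receives reminders and feedback without incentives; Arm 3 has electronic monitoring alone. On delivery it says: "With regard to the reminders and feedback in Arms 1 and 2, study participants will receive automated daily text message or push notification reminders". Table 1 and section 4.4 agree that Arms 1 and 2 get reminders and Arm 3 gets none.

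Appendix 1 supplies the texts under a single title, "Experiment phase text message reminders", followed by ten numbered messages. Neither the title nor any message carries an arm label. Reminder 8 first asks the parent to remind the child to take the medicine, then adds that "Each puff you take (as prescribed) gets you closer to your goal".

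Section 4.4 states that "study staff will help participants randomized to Arm 1 select an adherence reward goal", with a value of $30. No goal is described for Arm 2 or Arm 3.

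Section 2.1 sets the primary objective as to "determine the marginal effects of financial ICS incentives on adherence". Section 4.17 powers Arm 1 against Arm 3. It says that the Arm 1 versus 2 and Arm 2 versus 3 differences are not powered, but will give preliminary estimates of component effects to help power a later multicenter study.

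**The concern.** Arm 1 versus Arm 2 is the only contrast that separates the incentive from the reminders and feedback. It is cleanest when the two arms get the same reminders and differ only in the incentive. Reminder 8 does not fit that design well. Its goal has a clear referent in Arm 1 and none in Arm 2, and its image of progress with each puff matches how Arm 1 families are paid.

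An Arm 2 family could pass over the sentence, take it as encouragement, or infer that puffs earn something. The last reading is made somewhat easier because Arm 2 children do receive $10 for each Experiment month in which any actuation is recorded (sections 3.1.3 and 7.7.1), although section 7.7.1 states that this payment does not depend on adherence.

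What is at stake is how the preliminary component estimates are interpreted, and therefore what is carried into the planning of the next study.

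**Working it through.** **1. Does the wording match the Arm 1 incentive?** Inputs are from sections 3.1.3 and 4.4.

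- Four daily doses: 4 × $0.25 = $1 per day. Two daily doses: 2 × $0.50 = $1 per day.
- 30 days × $1 = $30, which equals the value of the Arm 1 reward goal.
- Each paid puff is therefore a fixed step toward the goal: $0.25/$30 = 1/120, or $0.50/$30 = 1/60.

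For Arm 1, reminder 8 is a literal description of the scheme. The other nine reminders are plain prompts, health facts or practical tips, and none mentions a goal or accrual.

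**2. How often would Arm 2 see it?** One message in ten over three 30-day months gives 90/10 = 9 exposures per family. This assumes even rotation and delivery by text. Section 3.1.3 also allows push notifications, whose wording is not given, so some families may never see it.

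**3. Which contrasts could move?** Let d be the unknown change in mean Arm 2 adherence caused by the wording; it may be positive or negative.

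- Arm 1 − Arm 2 changes by −d.
- Arm 2 − Arm 3 changes by +d.
- Arm 1 − Arm 3 changes by 0, because Arm 2 does not enter it.

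**4. Precision of the affected contrasts.** The plan's own figure comes first. Section 4.17 says: "To ensure a power of 80% at a significance level of 0.05 to detect a more conservative 30% difference in average adherence", with 65% against 35%. The unpooled two-proportion formula, two-sided, gives

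n = (1.960 + 0.842)² × (0.65 × 0.35 + 0.35 × 0.65) / 0.30² = 39.7, rounded up to 40 per arm.

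Allowing for 20% loss, 40/0.80 = 50, as stated. For Arm 2, 25 × 0.80 = 20 evaluable.

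The documents give no SD for the adherence proportion. The value implied by 40 per arm is 0.30 / (2.802 × √(2/40)) = 0.48. I take 0.25 to 0.48 as an assumed range. With 40 against 20 evaluable:

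| Assumed SD | SE = SD × √(1/40 + 1/20) | Difference detectable with 80% power = 2.802 × SE |
|---|---|---|
| 0.25 | 6.8 points | 19 points |
| 0.48 | 13.1 points | 37 points |

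The sample sizes are the same for Arm 2 versus Arm 3, so the same figures apply there. Nothing in the documents allows d to be estimated, but a small d would be hard to see against standard errors of this size.

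**The case against.** The strongest reply is that nothing documented has gone wrong. No passage states that reminder 8 is sent to Arm 2; that is inferred from the missing labels, and the platform could be programmed by arm. The sentence names no money or reward. It sits among messages about fewer attacks, better control and fewer missed school days, so a family never offered a reward could take the goal to be asthma control or taking doses as prescribed. If both arms receive the same text, reminder content is balanced. The affected contrasts are unpowered.

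Most of this stands, and it limits the point. A reader might infer that the incentive contrast is contaminated, or that the trial's main result is at risk. The documents support neither. They do not show that Arm 2 receives the message, how families would read it, or that it would change adherence. The powered comparison is Arm 1 versus Arm 3, and Arm 3 gets no reminders. Nor can it be assumed that Arm 2 families know others are paid per puff: section 7.1.2 says only that subjects are not blinded to conditions.

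The reply does not remove the inconsistency. If the list is shared, Arm 2 receives wording that fits only Arm 1. If reminder 8 is reserved for Arm 1, reminder content differs between arms and the protocol does not say so. Identical text is balanced in form but not in meaning when only one arm has the goal it mentions.

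**Conclusion.** The point holds as a minor one. On the natural reading of an unlabelled list, Arm 2 would receive a sentence that echoes Arm 1's per-puff reward. It may slightly blur Arm 1 versus 2 and, by the same amount in the opposite direction, Arm 2 versus 3. The direction and size are unknown and the size is probably small. The conclusion rests on two inferences: that the list serves both reminder arms, and that some families would connect the goal with a reward. A correction is still worthwhile because it costs almost nothing and settles what separates Arms 1 and 2.

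**What to change.** Preferred: in both arms, delete the goal sentence from reminder 8, or replace it with neutral text such as that of reminders 9 or 10. Reminder content and frequency are then identical, and Arms 1 and 2 differ only in the incentive. State in Appendix 1 that the list serves both arms, and apply the same neutrality to push wording if it is separate.

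Alternative, if the sponsor wants goal wording in Arm 1: label the message for Arm 1 only, describe it in section 3.1.3 as part of the incentive component, and send Arm 2 a neutral message in the same slot so that frequency stays equal. This adds a messaging difference to the monetary one, so the Arm 1 versus 2 estimate should then be described as the effect of the incentive together with its goal messaging.

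The cost is one line in Appendix 1 and one message setting in Way to Health, plus a sentence in section 3.1.3 under the alternative. Sample size and analysis are unchanged. If messages have already been sent, record which arms received reminder 8 and report it with the component estimates.
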